6.1.5. Analysis Visit Windows

Statistical analyses will be based on the windowing displayed in Table 1 (patients with a

treatment duration less than 8 weeks, i.e. < 56 days) and Table 2 (patients with a treatment duration of 8 weeks or more, i.e. >= 56 days).

However, imputation of missing data will be applied as described in Section 6.1.4.

Visit Name		Tougot dou	Analysis visit window			
		Target day	From SD	To SD		
Baseline				ded prior to the first dose apalumab		
Study Day 0 (free mapal		1	1	1		
Study	Day 3	4	2	5		
Study Day x		Study Day x + 1 day	Target day – 1 day	Target day + 1 day		
	Study Day n-1	Study Day x +1 day	Target day – 1 day	Day of last infusion of emapalumab		
a) EOT visit available	EOT / Week 8	EOT visit	Day of last infusion of emapalumab +1	EOT visit		
	EOT	EOT visit	EOT visit	EOT visit		
	Study Day n-1	Study Day x +1 day	Target day – 1 day	Day of last infusion of emapalumab – 1 day		
b) no EOT visit available	EOT / Week 8	Start day of last infusion *	Start day of last infusion *	End day of last infusion *		
	EOT	Start day of last infusion *	Start day of last infusion *	End day of last infusion *		

[figure not shown]
* Start and End date of infusion are in most of the cases the same date.

- a) If an EOT visit was performed and treatment duration was < 8 weeks (i.e. < 56 days), the day of EOT visit will be assigned as EOT/Week 8 analysis visit and as EOT visit prior to start of conditioning.
- b) If no EOT visit was performed and treatment duration was < 8 weeks (i.e. < 56 days), the day of last infusion will be assigned as EOT/Week 8 analysis visit and as EOT visit prior to start of conditioning.

		-	Analysis visit window			
Visit Name		Target day				
			From SD	To SD		
Baseli	ne		Last observation recorded prior to the first dose of emapalumab			
Study Day 0 (firs	t infusion of	1	1	1		
emapalur		1	1	1		
Study D	ć	4	2	5		
Study D	•	7	6	8		
Study D	•	10	9	11		
Study Da	2	13	12	14		
Study Da	2	16	15	17		
Study Da		19	18	20		
Study Da	•	22	21	23		
Study Da		25	24	26		
Study Da		28	27	29		
Study Da		31	30	32		
Study Da		34	33	35		
Study Da	•	37	36	38		
Study Da	2	40	39	41		
Study Day 37 Study Day 42		43	42	44		
Study Da	•	46	45	47		
Study Day 49 Study Day 48		49	48	50		
Week 8 is the last week prio			_	20		
	Study Day 51	52	51	Day of last infusion of emapalumab		
a) EOT visit available	EOT / Week 8	EOT visit	Day of last infusion of emapalumab + 1 day	EOT visit		
	EOT	EOT visit	EOT visit	EOT visit		
	Study Day 51	52	51	Day of last infusion of emapalumab - 1 day		
b) no EOT visit available	EOT / Week 8	57	Day of last infusion of emapalumab	Day of last infusion of emapalumab + 6 days		
	ЕОТ	Start day of last infusion *	Start day of last infusion *	End day of last infusion *		

Table 2: Treatment Visit Windows, treatment duration >= 8 weeks

Visit Name		Torget day	Analysis visit window				
		Target day	From SD	To SD			
Week 8 is not th	Week 8 is not the last week prior to EOT visit or last infusion (subsequent weeks (x to n))						
	Week x	Week (x*7) +1	Target day – 3 days	EOT visit – 1 day			
a) EOT visit available	EOT / Week 8	57	54	60			
EOT		EOT visit	EOT visit	EOT visit			
	Week x	Week (x*7) +1	Target day – 3 days	Day of last infusion of emapalumab – 1 day			
b) no EOT visit available	EOT / Week 8	57	54	60			
ЕОТ		Start day of last infusion *	Start day of last infusion *	End day of last infusion *			

* Start and End date of infusion are in most of the cases the same date.

If treatment duration was ≥ 8 weeks (i.e. ≥ 56 days) the visit within the analysis visit window of 54 and 60 days and closest to the target day will be assigned as EOT/Week 8 analysis visit.

- a) If an EOT visit was performed the day of EOT visit will be assigned as EOT visit prior to start of conditioning.
- b) If no EOT visit was performed the day of last infusion will be assigned as EOT visit prior to start of conditioning.

[figure not shown]

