5.3 DOSING SCHEMA

Emapalumab will be administered by IV infusion over a period of 1 to 2 hours depending on the volume to infuse, at a dose of 3 mg/kg. Infusions will be performed twice weekly (not more than 4 days apart), except for the second infusion which must be administered on SD3.

The 3 mg/kg dose will be maintained unless the Investigator, guided by the clinical and laboratory response in each patient, deems that a dose increase is appropriate: at any time during the study, it will be possible to increase emapalumab dose to 6 mg/kg (Table 3). A further dose increase to 10 mg/kg can be considered per Investigator's decision based on the patient's condition and appreciation of some benefit from the administration of emapalumab.

Upon achievement of Complete Response (i.e., normalization of all clinical and laboratory HLH parameters), the dose of emapalumab should be lowered to achieve 1 mg/kg twice a week and maintained until conditioning for transplant, as long as the patient's clinical conditions is satisfactory. Decrease of emapalumab dose will occur in a stepwise fashion (e.g. if patient was on 6 mg/kg, emapalumab will be administered in 3 mg/kg for at least one infusion before achieving 1 mg/kg).

Given the unpredictable course of the disease, in case of reactivation (e.g. triggered by intercurrent infections), subsequent dose increases to 3 mg/kg (and up to 6 or 10 mg/kg, as appropriate) may need to be considered and will be guided by the same clinical and laboratory parameters described above (Table 3).

The Investigators' assessments for emapalumab dose increase will be documented in the Dose Notification form (Appendix E) to be completed for each infusion and provided to Sponsor in a timely manner.

Upon regaining a Complete Response, the dose of emapalumab should be lowered again to achieve 1 mg/kg twice a week. Should HSCT be scheduled beyond 12 weeks from emapalumab initiation, for reasons unrelated to the administration of emapalumab (e.g., lack of donor availability), and provided Complete Response is maintained, the treatment with emapalumab may continue at the dose of 1 mg/kg once a week.

The duration of treatment is foreseen until the start of conditioning for HSCT, but must not exceed 6 months. The minimum treatment duration is 4 weeks, if the patient's conditions and donor availability allow the performance of HSCT.

No wash-out period is required between the last administration of emapalumab and the start of conditioning.

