8 OUTLINE OF STUDY PROCEDURES

Patients will be recruited from specialized study sites, equipped with an intensive care unit and access to a bone marrow transplant unit.

Patients will be in the treating unit the day before the first administration of emapalumab (Study Day minus one, SD-1).

For a detailed description of the schedule of visits and assessments, refer to the Schedule of Assessment Table 1 (Screening and Treatment Period) and Table 2 (Follow-up Period).

Informed consent form must be signed by the patient or his/her legally authorized representative prior to any study-related procedures, with the assent of patients who are deemed suitable to provide it.

During the emapalumab treatment period, visits for infusion and efficacy/safety assessments will occur on SD0, SD3 and twice-a-week thereafter (not more than 4 days apart). In the circumstances when HSCT is scheduled beyond 12 weeks from emapalumab initiation and Complete Response is maintained (see Section 5.3), the treatment with emapalumab may continue once a week; acceptable time-window for visits in this case will be ± 1 day. An EOT visit has to be performed 3 ± 1 days after last emapalumab infusion.

Furthermore, during the follow-up period, the following time-windows are allowed around visits:

- Pre-conditioning: can be combined with EOT visit provided the two visits are

not more than 2 days apart

Week (Wk) 1-2-3, D+30 post-HSCT: ±2 days
 D+60, D+100 post-HSCT: ±1 week
 6-mo, 1-yr post-HSCT: ±4 weeks

If HSCT is not performed, the described schedule applies to the follow-up visits required to occur after the last emapalumab infusion.

Following windows can be applied to the vital signs measurement:

When measured every 15 minutes: ±5 minutes
 When measured every 30 minutes: ±10 minutes

- When measured at 1 hour and 2 hours after infusion: \pm 15 minutes

Some procedures are not to be done systematically but only if clinically relevant. For example:

- ECG is mandatory at Screening and at EOT visits, however it should be done at any other timepoint during the study, if deemed appropriate.
- Brain magnetic resonance imaging (MRI) is mandatory at Screening only in case of CNS disease, but should be done at any other time-points during the study to monitor evolution or to confirm onset of CNS involvement, as clinically indicated.

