6.1.9. Derived Variables

6.1.9.1. General

• Sponsor defined study day = date of interest – date of first emapalumab infusion

[figure not shown]
Note: This study day will be used in the analysis visit windowing and displayed on listings if required. Study Day 0 (SD0) is the day when first emapalumab infusion is performed.

• Change from baseline = value at current time point – value at baseline.

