6.1.9.3. Safety Parameters

Table 4: Definition of Drug Administration Variables

Statistics for Exposure (dosing)	Derivation
Duration of exposure (days)	Date of last infusion of emapalumab – date of first infusion of emapalumab + 1
Duration of exposure (weeks)	Duration of exposure (days)/7
Maximum dose prescribed	Maximum of all doses prescribed (mg/kg)
Cumulative dose (mg/kg)	Sum of total actual dose per kg administered from first infusion date until last infusion date
Average dose frequency (days)	Duration of exposure (days)/ total number of infusions
Average dose of emapalumab per day (mg/kg)	Cumulative dose (mg/kg)/ duration of exposure (days)
Percentage of dose increases from baseline dose	(Number of dose increases from baseline dose / number of total doses) multiplied by 100.
Percentage of dose decreases from baseline dose	(Number of dose decreases from baseline dose / number of total doses) multiplied by 100.

Table 5: Definition of Adverse Events

Variable	Definition
Adverse Event (AE)	All recorded AEs (collection of AEs starts after ICF signature).
Treatment-Emergent Adverse Event (TEAE)	Any AE (serious and non-serious) with an onset date after the start of the first emapalumab infusion.
Pre-conditioning AE	Any AE (serious and non-serious) with start date before the start of conditioning for HSCT*.

[figure not shown]

Variable	Definition			
Post-conditioning AE	Any AE (serious and non-serious) with start date after the start of conditioning for HSCT*.			
TEAEs related to the study drug	Any AEs with an onset date after the start of the first emapalumab infusion with "Relationship to Study Drug" of "Related".			
Serious TEAEs	Any AEs with an onset date after the start of the first emapalumab infusion with "Serious" of "Yes".			
TEAEs leading to withdrawal of study drug	Any AEs with an onset date after the start of the first emapalumab infusion with "Action taken with study drug" of "Drug Withdrawn".			
TEAEs resulting in death	Any AEs with an onset date after the start of the first emapalumab infusion with "Results in death" of "Yes".			
TEAE with infections	Any AE with an onset date after the start of the first emapalumab infusion with system organ class (SOC) 'Infections and Infestations' or in the HLGT 'Microbiology and serology investigations'.			

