8.2.6. Clinical Response

Assessment of Clinical Response using the response categories seen in Table 6, will be described using counts and percentages at each visit.

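### SAP Table 2 visit windows do not fit twice-weekly dosing: days 51–53 have no window for patients treated past Week 8, later weekly windows are nested, and the 3-day grid leaves gaps

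*SAP*

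**What the plan says.** **Schedule.** Protocol 5.3: "Infusions will be performed twice weekly (not more than 4 days apart), except for the second infusion which must be administered on SD3". Protocol section 8 ties the assessment visits to the same calendar; they "will occur on SD0, SD3 and twice-a-week thereafter (not more than 4 days apart".

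**Which table applies.** SAP 6.1.5: "Statistical analyses will be based on the windowing displayed in Table 1" for shorter courses. The longer ones use "Table 2 (patients with a treatment duration of 8 weeks or more, i.e. >= 56 days".

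**Table 2 up to day 50.** Day 1, then days 2–5 (target 4), then a window every 3 days at target ± 1: 6–8, 9–11, and so on to 48–50.

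**Table 2 after day 50.** There are two blocks.
- Week 8 is the last week: a *Study Day 51* row starts at day 51, followed by EOT/Week 8 and EOT.
- Treatment continues past Week 8: there is no *Study Day 51* row. EOT/Week 8 is days 54–60. A single *Week x* row has target 7x + 1 and lower limit target − 3. Its upper limit is "EOT visit – 1 day", or the day before the last infusion if there was no EOT visit.

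**Choice among values.** SAP 6.1.4 takes the value closest to target within a window. It has no rule for one value that lies in several windows.

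**Day numbering.** SAP 6.1.9.1: "Study Day 0 (SD0) is the day when first emapalumab infusion is performed", and this numbering is to be used for the windows. The From/To SD columns of Table 2 give that day the number 1.

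**Use.** Clinical signs (SAP 8) and laboratory shifts (SAP 10.2.1) are summarised by visit. Clinical response (SAP 8.2.6) "will be described using counts and percentages at each visit".

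**The concern.** Two visits every 7 days cannot line up with a window every 3 days. Patients on different weekday patterns will then be missing from different windows, so neighbouring columns of a by-visit table describe different subsets. Percentages use the whole analysis set as denominator by default (SAP 4.1), and the shift tables do so explicitly (SAP 10.2.1). An empty window therefore lowers a rate without any clinical reason.

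The other two defects bear on where a value goes. A visit on days 51–53 in a continuing patient has no place in the tables. A weekly window with no upper limit of its own can report, for example, a Week 10 value as Week 9. A programmer would have to settle both questions outside the SAP.

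**Working it through.** **Inputs.** Schedule: Protocol 5.3 and 8. Window limits: SAP Table 2. Days are first counted from 1, as in the table's target column (day = SD + 1).

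**Reproducing the grid.** Day 1, days 2–5, then targets 7, 10, ..., 49 at ± 1 give 2 + 15 = 17 windows up to day 50. This matches the printed limits. The *Study Day 51* row would be the 18th.

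**Regular calendars.** Twice-weekly dosing with SD3 fixed and gaps alternating between 3 and 4 days gives two patterns, each with 16 infusions in 8 weeks:
- A: SD0, 3, 7, 10, 14, ..., 49, 52, i.e. days 1, 4, 8, 11, 15, ..., 50, 53
- B: SD0, 3, 6, 10, 13, ..., 48, 52, i.e. days 1, 4, 7, 11, 14, ..., 49, 53

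**1. Days 51–53.** For a patient continuing past Week 8, the windows go from 48–50 directly to 54–60. SD52 is day 53 on both calendars and is unassigned. Counted from 0 it is day 52, also unassigned. If SD52 is instead the last infusion, SAP Table 4 defines duration of exposure as "Date of last infusion of emapalumab – date of first infusion of emapalumab + 1", which gives 52 − 0 + 1 = 53 days. That is below 56, so Table 1 applies and covers it.

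**2. Weekly windows.** The lower limit is 7x + 1 − 3 = 7x − 2 and the upper limit is the same for every x.

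| Week | Target | From | To |
|---|---|---|---|
| 9 | 64 | 61 | EOT − 1 |
| 10 | 71 | 68 | EOT − 1 |
| 14 | 99 | 96 | EOT − 1 |

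- Day 100, in a course with a later EOT visit: 7x − 2 ≤ 100 gives x ≤ 14, so Weeks 9 to 14, six windows.
- EOT visit on day 183: day 182 lies in Weeks 9 to 26, i.e. 26 − 9 + 1 = 18 windows.

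Clinical response is assessed every 2 weeks (Protocol Table 1 and 8.4). Suppose the assessments fall at Weeks 10, 12 and 14 (days 71, 85, 99). Week 9 has no value on days 61–67. The closest value to its target of 64 inside the printed window is day 71, so that one assessment is reported for both Week 9 and Week 10. Day 85 likewise fills Weeks 11 and 12.

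**3. Empty windows.** By day 50, each calendar has 15 infusions for 17 windows. A 3-day window cannot hold two infusions that are 3 days apart, so 17 − 15 = 2 windows are empty.

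| Calendar | Days counted from 1 | Days counted from 0 |
|---|---|---|
| A | 12–14 and 33–35 | 18–20 and 39–41 |
| B | 15–17 and 36–38 | 21–23 and 42–44 |

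Counted from 0, as in SAP 6.1.9.1, the first infusion also misses its own window (From 1 To 1).

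As a check on irregular spacing, all sequences of 3- and 4-day gaps through SD55 were enumerated against the 18-window version. They leave 0 to 4 windows empty, most often two (33,748 of 51,217 sequences). These are counts of sequences, not probabilities.

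**Size in a table.** With 34 to 41 patients (SAP 3.2), each patient without a value in a window lowers a whole-set percentage by up to 1/34 = 2.9 or 1/41 = 2.4 points.

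**Primary endpoint.** The Week 8 Assessment Visit is 3 days after the last Week 8 infusion (Protocol 8.5): SD52 + 3 = SD55, i.e. day 56. That lies in 54–60, and so does 55 if days count from 0.

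**The case against.** The best case for the plan has four parts.

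- **The intent can be guessed.** In SAP Table 1, and in the block for patients whose last week is Week 8, an open limit appears only on the last row before EOT, and ordinary rows are target ± 1. The *Week x* row was probably meant the same way. That is plausible, but the block is labelled as covering all subsequent weeks and prints only the open form, with and without an EOT visit.
- **The closest-to-target rule protects the data.** It does where a week has its own value, which will be usual for laboratory tests done at each infusion. It does not protect assessments made every 2 weeks.
- **Empty windows matter less than they seem.** The planned response table is the investigator's assessment, which would be missing from most 3-day windows on any infusion grid. For clinical signs, the windows apply only when no value exists on the specified day (SAP 6.1.4). Continuous summaries show the number of non-missing values. This stands, and limits that part mainly to the shift tables and, to a lesser extent, the clinical signs.
- **Nothing inferential depends on it.** This also stands.

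A reader might go further and infer that the same two windows are always empty, that the second Week 8 infusion never has a window, or that the dexamethasone summaries are distorted. The documents do not support these readings. The protocol fixes only SD3 and a maximum gap of 4 days. Table 1 and the last-week block of Table 2 do cover SD52. Steroid dose is derived from medication records with dates and frequencies (SAP Table 14 and 16.1), so harm there is not shown.

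**Conclusion.** Wrong as written, of minor severity. For patients treated past Week 8, three days (51–53) have no window, and a regular schedule puts an infusion visit there under either day count. All weekly windows after Week 8 are nested, so weeks without their own value are filled with later ones. On a regular 3/4-day calendar, two of the 17 windows up to day 50 are empty.

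This rests on three assumptions: regular alternating gaps for the count of two, two-weekly response assessments continuing after Week 8, and treatment duration in SAP 6.1.5 meaning the duration of exposure in SAP Table 4.

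It would be tempting to read this as a threat to the efficacy result, but the documents do not bear that out. The primary endpoint has its own EOT/Week 8 window and an 8-day imputation rule. Time to response and duration of response use all scheduled and unscheduled visits (SAP 6.1.4). All collected data are listed. The damage is confined to descriptive by-visit tables.

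**What to change.** Revise SAP Table 2 before database lock:

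1. **Weekly windows.** End *Week x* at the earlier of target + 3 days and the present limit (EOT visit − 1, or last infusion − 1). Week 9 becomes 61–67 and Week 10 becomes 68–74, following on from 54–60 without overlap.
2. **First 8 weeks.** Summarise by nominal infusion number, or use a twice-weekly grid with targets 1, 4, 8, 11, 15, ..., 50, 53. One contiguous version keeps day 1 and days 2–5, then for k = 1 to 7 uses days 7k − 1 to 7k + 2 and 7k + 3 to 7k + 5 (6–9, 10–12, 13–16, ..., 48–51), with the last window cut to 52–53. That is 2 + 14 = 16 windows for 16 visits. None is empty on calendar A or B, and days 51–53 are covered for continuing patients. Apart from day 54, which stays in the Week 8 window, it also accommodates the ± 1 day that Protocol section 8 allows for laboratory tests.
3. **Day numbering.** Bring the From/To SD columns into line with the SD0 definition in SAP 6.1.9.1.
4. **Leave unchanged** the EOT/Week 8 window of days 54–60.

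Weekly windows of target ± 3 throughout would look simpler but are not recommended. They put day 53 in Week 7 (50 ± 3 = 47–53) and merge SD0 with SD3 (1 ± 3 reaches day 4).

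Cost: a SAP table edit and reprogramming of the descriptive tables. No new data are needed and the primary analysis does not change.

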3.3 TREATMENT PERIOD

The duration of treatment is foreseen until the start of conditioning for HSCT, but must not exceed 6 months.

The minimum treatment duration is 4 weeks, if the patient's conditions and donor availability allow for HSCT.

No wash-out period is required between the last administration of emapalumab and the start of conditioning.

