The following assessments are to be performed post-infusion at Visit 3 and onwards:

Vital sign assessment:

 Heart rate, oxygen saturation, blood pressure and temperature at the end of the infusion, 1 hour and 2 hours after completion of emapalumab infusion

PK:

 Emapalumab serum concentration (every other infusion starting from Visit 3)

Clinical Assessment:

 QOL questionnaire - PedsQL[™], Pediatric Quality of Life Inventory[™] (at Visit 3 only)

During treatment, emapalumab and biomarker concentrations may be measured in other matrices, such as CSF or BAL, if samples obtained in procedures which are performed for diagnostic/therapeutic purposes can also be available for these exploratory investigations, and if clinically indicated.

8.5 WEEK 8 ASSESSMENT VISIT (3 DAYS AFTER WEEK 8 INFUSION) AND END OF TREATMENT VISIT (3 DAYS AFTER LAST EMAPALUMAB INFUSION)

These visits will include a full patient's assessment.

The Week 8 Assessment Visit will be performed 3 (± 1) days after the last Week 8 emapalumab infusion. If treatment with emapalumab is completed before Week 8, only an EOT visit will be performed 3 (± 1) days after the last infusion.

For patients continuing treatment beyond Week 8, an EOT visit will be conducted 3 (± 1) days after the last emapalumab infusion.

The following assessments are to be performed at the Week 8 Assessment Visit and at the EOT Visit:

Clinical Assessment:

- Vital signs, including body temperature, heart rate, blood pressure, and oxygen saturation
- Physical examination, including as a minimum, weight, spleen and liver size (by abdominal palpation), and neurological examination
- Assessment of clinical response
- QOL questionnaires PedsQL[™], Pediatric Quality of Life Inventory[™],
 BASES (BASES only at EoT and if HSCT is planned)

Procedure:

ECG (only at EOT)

Search for infections:

- TB by PCR (if not performed within the last 4 weeks)
- Infection search & monitoring in case of suspicion of infection or if there is an active infection at screening/baseline to monitor evolution of viral load and positivity for an identified pathogenAtypical mycobacteria, Histoplasma Capsulatum, Shigella, Salmonella, Campylobacter, Leishmania – only if an infection is suspected

Study NI-0501-09 NI-0501 in Primary HLH Page 54 of 92

Laboratory:

 CBC with differential count (including large unstained cells count, whenever performed as routine)

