8.6.1 Follow-Up Pre-HSCT: Pre-Conditioning Visit

The following assessments have to be performed before starting the administration of conditioning agents for HSCT. This visit can be combined with the EOT visit, if the visits are not more than 2 days apart.

If the pre-conditioning and EOT visits are not combined, the following assessments are to be performed:

Study NI-0501-09 NI-0501 in Primary HLH Page 55 of 92

Clinical Assessment:

- Vital signs, including body temperature, heart rate, blood pressure, and oxygen saturation
- Physical examination, including as a minimum, spleen and liver size (by abdominal palpation), height/length and neurological examination
- Survival

Laboratory:

- CBC with differential count (including large unstained cells count, whenever performed as routine)
- Coagulation tests: activated partial thromboplastin time and/or ratio, prothrombin time and/or INR, D-dimers, and fibrinogen
- Biochemistry: glucose, ferritin, CRP, liver function (AST, ALT, γGT, LDH, ALP, bilirubin), renal function (albumin, creatinine and urea) and triglycerides (fasting whenever possible)
- Urinalysis: glucose, blood, protein, leucocytes, ketones, pH, gravity

Imaging:

- Abdominal ultrasound with spleen longitudinal measure
- Chest X-ray. Other imaging modalities (e.g. CT) performed as part of pre-transplant work-up are also acceptable.

Safety:

Recording of any AEs occurred since last visit

PK:

- Emapalumab serum concentration
- PD: CXCL9, CXCL10, sCD25, total IFNγ.

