For a given AE, the assessment of its intensity should reflect the highest grade (on the three-point scale mentioned above) reported during its course (except when the intensity of a pre-treatment AE increases after treatment initiation, as indicated above).

The relationship of AEs to the IMP will be assessed by the Investigator using a "Yes/No" classification. A "Yes" relationship infers that there is a reasonable suspected causal relationship to the IMP. The

Study NI-0501-09 NI-0501 in Primary HLH Page 59 of 92

expression "reasonable causal relationship" is meant to convey that there are facts, evidence or arguments to suggest a causal relationship. In this study, emapalumab is the only IMP.

Specific situations:

- Common HLH signs and symptoms (e.g., anemia, neutropenia, thrombocytopenia, pancytopenia, splenomegaly, hepatomegaly) will not be reported as separate AEs unless clearly attributed to a cause different from HLH, and the verbatim term should indicate the cause.
- If changes in the above mentioned HLH signs and symptoms indicate HLH worsening or reactivation, worsening or reactivation will be reported as an AE.
- Fever will only be reported when not linked to an identified cause with the highest temperature considered during the period. If it is a recurrent fever it can be entered as intermittent fever with no need to specify the temperature (the intensity should be a reflection of the highest temperature observed). If fever is considered as a sign of a confirmed infection or of HLH worsening or reactivation, only the diagnosis should be reported as an AE, and not `fever`.
- Viral load positivity, in particular for EBV, CMV and adenovirus, and evolution will be collected on a dedicated eCRF module.
- Active infections will be reported as AEs, indicating whether constituting a primary infection or a reactivation (whenever possible). Pathogen positivity and evolution will be collected in a dedicated eCRF module.
- Expected effects of conditioning (i.e., pancytopenia during conditioning and until engraftment) will not be reported.

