6.1.4. Handling of Dropouts or Missing Data

[figure not shown]
While all possible efforts will be made to ensure that patients stay in the study and all data is collected as scheduled, the occurrence of missing data cannot be completely eliminated.

Rules for handling missing or partial AEs or birth dates are described in Section 6.1.10

For defining the primary efficacy endpoint (Overall Response, see Section 6.1.9.4 for definition), values of some parameters may be missing, thus impacting the response assessment. Imputation rules for assessing disease response at EOT or Week 8 (whichever occurs earlier) and throughout the study have been pre-defined as follows. Note: Imputed values will be flagged in the listings for all endpoints where applicable.

Response at EOT or Week 8 (whichever occurs earlier):

- Missing data at EOT/Week 8 for the parameters relevant to assessment of Overall Response will be imputed by the closest available value from the EOT/Week 8 target day (as per Table 1 and Table 2) up to 8 days, provided upper window limit is before start of conditioning. For body temperature, in the event of repeated measures recorded on the same study day, the highest value will be selected.
- No imputation will be applied if no value is available within the time of the EOT/Week 8 target day up to 8 days. That parameter will be viewed as missing and complete response will not be assigned, even if all other parameters are normal.
- Values recorded at both scheduled and unscheduled visits will be considered.

• If all parameters are unable to be imputed then the overall response assessment will be recorded as missing.

Response throughout the study:

- For secondary time to event analyses (e.g., duration of response, time to response), both scheduled and unscheduled visits will be used for assessment of response.
- If a numerical parameter (i.e. Body Temperature, D-Dimer, Fibrinogen, Ferritin, Platelets, Neutrophils) needed for the response assessment is missing, the midpoint approach will be used to estimate the missing value i.e., the last observed value before the missing period will be averaged with the first value available after the missing period. This rule will be applied to parameter values missing for a period of up to a maximum of 7 consecutive days.

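### SAP 6.1.5 sets no conditioning cut-off for observed EOT/Week 8 values, so the primary endpoint can be scored on data taken after transplant conditioning has begun

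*SAP*

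**What the plan says.** **Treatment and visits.** Protocol 3.3 states: "The duration of treatment is foreseen until the start of conditioning for HSCT, but must not exceed 6 months". It adds: "No wash-out period is required between the last administration of emapalumab and the start of conditioning". Protocol 8 states: "An EOT visit has to be performed 3 ± 1 days after last emapalumab infusion". Of the Pre-Conditioning visit, Protocol 8.6.1 says: "The following assessments have to be performed before starting the administration of conditioning agents for HSCT". Protocol 8, 8.6.1 and Table 2 allow this visit to be combined with the EOT visit if the two are not more than 2 days apart. None of them requires it.

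**Choice of the primary-endpoint assessment.** For treatment under 56 days with an EOT visit, SAP 6.1.5 (Table 1, rule a) says: "the day of EOT visit will be assigned as EOT/Week 8 analysis visit and as EOT visit prior to start of conditioning". The window runs from the day after the last infusion to the EOT visit. In Table 2 (56 days or more), the rows where Week 8 is the last week use the same window if there is an EOT visit. If there is none, the window runs from the last infusion to 6 days after it.

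**Where conditioning does act as a limit.** In SAP 6.1.4, missing EOT/Week 8 values may be imputed from nearby days, "provided upper window limit is before start of conditioning". SAP Table 12 ends the observation period for duration of response at the start of conditioning.

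**Effect of conditioning.** Protocol 9.2.1 says: "Expected effects of conditioning (i.e., pancytopenia during conditioning and until engraftment) will not be reported". SAP Table 19 lists etoposide, antithymocyte immunoglobulin and alemtuzumab among the conditioning drugs. Protocol section 4 names the same three as conventional HLH therapy.

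**The concern.** The primary endpoint is meant to describe disease control on emapalumab at EOT or Week 8. Once conditioning has begun, neutrophils and platelets may fall because of it, and other HLH criteria may improve because of drugs that also treat HLH. An assessment made then no longer isolates emapalumab.

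The plan makes the overlap easy to reach. Infusions are twice weekly and not more than 4 days apart (Protocol 5.3). A patient who keeps that schedule up to conditioning therefore starts it within about 4 days of the last infusion. The minimum treatment duration is 4 weeks, so transplant before Week 8 is a planned route.

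The SAP protects a missing value from conditioning but not an observed one. This is also the only endpoint with a formal test.

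**Working it through.** **1. Date arithmetic.** Let L be the day of the last infusion. The EOT visit is due at L+3±1, that is L+2, L+3 or L+4. A visit on the day conditioning starts is counted as on or after it, because dates alone do not show which came first.

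| Conditioning starts | In-window EOT days on or after that start |
|---|---|
| L, L+1 or L+2 | all three |
| L+3 | L+3 and L+4 |
| L+4 | L+4 only |
| L+5 or later | none |

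Example: with conditioning at L+1, the nominal EOT visit (L+3) comes 2 days after conditioning starts. Rule a still makes it the primary-endpoint visit. A Pre-Conditioning visit at L+1 is 2 days from L+3 and could be combined with it. One at L is 3 days away and could not, unless EOT is held at L+2. Combining helps in some of these cases and is never mandatory.

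**2. The closing words of rule a.** They can be read in two ways.
- As a label for the visit's second role, they exclude nothing.
- As a condition, they leave a gap. Rule b (day of last infusion) applies only when no EOT visit was performed, so an EOT visit made after conditioning began has no rule.

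**3. Table 2.** The text beneath it picks the visit closest to target within days 54 to 60, which differs from the rows where Week 8 is the last week. Neither the text nor those rows has a conditioning limit.

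**4. The plan's own figures.** Inputs from Protocol 11.1: n=34, null 40%, alternative 65%, exact binomial test, one-sided 0.025, stated power 85%. The smallest r with P(X≥r | 34, 0.40) ≤ 0.025 is 20.
- P(X≥20 | 34, 0.40) = 0.0205, so 20/34 passes.
- P(X≥19 | 34, 0.40) = 0.0444, so 19/34 fails.
- P(X≥20 | 34, 0.65) = 0.826. The stated 85% is not reproduced by the exact test. The normal approximation gives n=33.85, hence 34. That mismatch is a separate matter and does not bear on this point.
- One patient is 1/34 = 2.9 percentage points.

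**5. Illustration.** The documents do not give the share affected, so both inputs here are assumptions: f is the share of patients scored after conditioning starts, and m is the chance that such a score flips. If only responders flip, the response rate is 0.65(1−fm). If only non-responders flip at a true 40%, it is 0.40+0.60fm.

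| f | m | Rate, responders flip | Power | Rate, non-responders flip | Type I error |
|---|---|---|---|---|---|
| 0 | – | 0.650 | 0.826 | 0.400 | 0.0205 |
| 10% | 25% | 0.634 | 0.769 | 0.415 | 0.031 |
| 20% | 50% | 0.585 | 0.558 | 0.460 | 0.092 |
| 30% | 50% | 0.552 | 0.405 | 0.490 | 0.165 |

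These rows show sensitivity, not expected effects.

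**6. Planned sensitivity analyses (SAP 8.1).** None isolates this problem. Analyses 3 and 4 count other concomitant HLH treatment as non-response but do not say whether conditioning drugs qualify.

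**The case against.** The best reply is that the intended order is clear. EOT closes the treatment schedule, the Pre-Conditioning visit opens follow-up, and conditioning comes after that. Protocol Table 2 prints EOT first, the two visits may be merged when close together, and rule a itself speaks of a visit before conditioning. This stands as evidence of intent, but intent does not move a visit. When conditioning starts within 2 days of the last infusion, the 3±1 day rule places EOT on or after that start unless the site chooses to combine.

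A second reply also has weight. Neutrophils and platelets form a single cytopenia item. Partial Response and HLH Improvement generally need three abnormalities normalised or improved, so losing that item often leaves Overall Response intact. The protocol also gives no time course showing that counts fall within the few days at issue.

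Third, affected patients could be traced: SAP 10.2.1 flags laboratory values as pre- or post-conditioning, and SAP 10.8 lists conditioning dates. No planned analysis uses this information.

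A reader might infer more than the documents support:
- **That the error penalises the patients doing best.** No net direction is established, because conditioning drugs active against HLH could also create a response.
- **That each affected patient costs 2.9 points.** That holds only where the changed criterion decides Overall Response.
- **That the carry-forward rule in SAP 6.1.4 brings in later data.** It uses only values from before the gap.
- **That the midpoint rule contaminates response at start of conditioning.** Its block is introduced for secondary time-to-event analyses, and SAP 8.2.3 refers that endpoint to the primary methods. A gap spanning the start of conditioning would also require the scheduled Pre-Conditioning laboratory tests to be missing.

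**Conclusion.** The point holds as a gap in the SAP's visit-assignment rules. Followed as written, they can score the only formally tested endpoint on values taken under conditioning, while the SAP's own limit covers imputed values only.

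The exposed patients are those whose last infusion is at or before Week 8 and who start conditioning within 4 days of it: certainly at 0 to 2 days unless the visits are combined before conditioning, and possibly at 3 or 4 days. In the Table 2 row without an EOT visit, where the window runs to 6 days after the last infusion, exposure can extend to 6 days.

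The documents do not give the number of such patients, the direction of bias is open, and some contaminated values will not change the outcome. The consequence could still be decisive, since one patient separates 20/34 (p=0.0205) from 19/34 (p=0.0444). The power and error figures above rest on assumed shares and flip rates. The gap is worth closing before database lock. The documents do not support a claim that the primary result is biased by a known amount.

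**What to change.** **SAP 6.1.5, all EOT/Week 8 windows in Tables 1 and 2 and the text beneath them.** Use no value recorded after the start of conditioning for any response criterion. If the EOT visit falls on or after the start of conditioning, use the last available assessment before it, normally the Pre-Conditioning visit. List the patients to whom this applies.

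**SAP 6.1.4, for consistency.** Do not let the midpoint rule use a value recorded after the start of conditioning. The carry-forward rule needs no edit.

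**Cost.** SAP wording and programming before database lock. The Pre-Conditioning visit already collects temperature, spleen size by palpation and ultrasound, neurological examination, blood counts, coagulation, ferritin and sCD25 (Protocol 8.6.1). The downside is small: a few patients are assessed 1 to 3 days earlier, for example at L to L+2 instead of the nominal L+3. The design figures do not change, and no change to the timing of infusions, visits or conditioning is needed.
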